## STUDY PROTOCOL AND STATISTICAL ANALYSES

### Study Population

Our study adhered to the Helsinki Declaration developed by the World Medical Association for medical research involving human material and data. The study protocol was approved by the University of Health Sciences Hamidiye Scientific Research Ethics Committee. Written informed consent was obtained from the participants. The trial was registered at clinicaltrials.gov (NCT04334681). This study retrospectively reviewed the data of 313 patients, older than 18 years, who underwent unroofing curettage (UC) and rhomboid excision and MLF surgeries at Konya Training and Research Hospital between January 2013 and January 2017.

Patients with common gluteal pilonidal disease, collagen tissue disease, and irregular diabetes mellitus were excluded. The data of 278 patients who did not have deficiencies in file and follow-up information were divided into the UC group (n, 135) and rhomboid excision and MLF group (MLF group; n, 143) and analyzed.

### Preoperative antibiotic prophylaxis and anesthesia type

The hospital staff shaved all patients' hair around the natal cleft just before surgery. No antibiotics were used in either group.

Patients in the MLF group were operated on under spinal anesthesia. In the UC group, patient preference and the anesthetist's recommendation determined the type of anesthesia that was used. The local anesthetic agent was 2% prilocaine hydrochloride diluted with distilled water in a 1: 2 ratio. The patients who had reservations with local anesthesia were operated under spinal anesthesia.

## Surgical procedure

The same surgeon performed all operations in the UC group. Operations in the MLF group were performed by another surgeon who conducted the study.

During both procedures, patients were placed in the prone position; the buttocks' cheeks were pulled laterally with adhesive tape, providing good exposure of the intergluteal area. The surgical site was disinfected with povidone-iodine solution.

**Unroofing curettage procedure:** A probe was passed through the sinus orifices for guidance; the skin was cut and the roof was opened. The hairs and necrotic debris in the sinus cavity were removed. Curettage was performed without excising the granulation tissue at the pit's base because excessive excision delays healing. We achieved hemostasis with monopolar diathermy. A drain was not used in this procedure. The cavity was filled with fine gauze soaked in standard saline solution (0.9% sodium chloride) as much as possible, and the dressing was closed

**Modified Limberg flap procedure:** Pilonidal cyst and flap lines were marked with a sterile skin pen. The lower end of the rhombus was 1.5 cm lateral to the midline. The size of the fasciocutaneous flap was equal to the size of the rhombus. Under the guidance of methylene blue, the rhombus was excised up to the presacral fascia, and the fasciocutaneous flap was transposed medially. A suction drain was placed under the flap. Subcutaneous tissue was approximated with 2-0 absorbable braided polyglactin sutures. The skin was sutured with 3-0 nonabsorbable monofilament polypropylene stitches. Depending on the amount of discharge, the drain was removed on postoperative day 3 or 4. Sutures were removed 2 weeks postoperatively

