## Postoperative care

Patients who underwent the surgery under local anesthesia were discharged on the same day. Patients on whom spinal anesthesia was used stayed in the hospital for 1 or more days.

Antibiotics were not given to the patients in either group. An analgesic containing diclofenac sodium (50 mg bid) was prescribed, and patients were recommended to take it if they experienced pain.

Dressings were changed in the outpatient clinic for the first 3 days in the UC group. Afterward, the process of dressing was explained to the patient's relatives, and the dressing process was continued at home. We called the patient for follow-up at 7–10-day intervals.

In the MLF group, the wound was checked at 2-day intervals after discharge from the hospital. The surgeon removed the sutures after observing for complete wound epithelization. All patients in either group were followed up for wound complications for 1 month after discharge from the hospital.

Patients were contacted via telephone for follow-up at 6 months and 1 year postoperative. Following this, they were then contacted for an annual check. The patients were questioned regarding their degree of satisfaction with the surgery and the postoperative results (graded as excellent, good, not bad, and bad). Surgeons recorded information on treatment, the healing process, follow-up examinations, readmission, reoperation, and revision on follow-up forms.

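### Does the plan need changing because each operation had its own surgeon, so that technique and surgeon cannot be told apart?

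*Combined protocol and SAP*

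**What the plan says.** **Design.** Study Population describes a retrospective review of 313 patients. The 278 with complete files were grouped by the operation they had received (135 UC, 143 MLF). No allocation rule is given.

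**Surgeon.** Under Surgical procedure: "The same surgeon performed all operations in the UC group", and "Operations in the MLF group were performed by another surgeon who conducted the study".

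**Anaesthesia.** Under Preoperative antibiotic prophylaxis and anesthesia type: "Patients in the MLF group were operated on under spinal anesthesia". In UC the type depended on what the patient wanted and the anaesthetist advised: "The patients who had reservations with local anesthesia were operated under spinal anesthesia". The local/spinal split is not given.

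**Discharge and early follow-up.** Postoperative care ties discharge to anaesthesia: "Patients who underwent the surgery under local anesthesia were discharged on the same day" and "Patients on whom spinal anesthesia was used stayed in the hospital for 1 or more days". After discharge, "In the MLF group, the wound was checked at 2-day intervals after discharge from the hospital". UC patients had clinic dressings for the first three days, and then "We called the patient for follow-up at 7–10-day intervals". The same section gives both groups one month of wound surveillance after discharge, then telephone contact at 6 months, at 1 year and annually.

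**Analysis.** Statistical analyses names Mann–Whitney, chi-square and Fisher exact tests at p < 0.05. It mentions no adjustment, stratification or matching. No section states what the UC versus MLF contrast can support.

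**The concern.** The groups are labelled by operation and compared by simple two-group tests, so a reader may take p < 0.05 as evidence about the operation. The same p-value could come from the surgeon, the anaesthesia, the choice of patients for each operation, the frequency of wound checks, or the way each surgeon filled in the follow-up forms.

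What is at stake can be illustrated, though only with assumed rates. Suppose technique has no effect and the surgeon alone moves a complication rate from 10% to 20%. With 135 and 143 patients, the chance of a two-sided p < 0.05 would be about 64% (shown in the working). The documents give no outcome rates, so this shows how the problem could act and does not estimate a bias in this study.

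**Working it through.** The plan states no sample-size or power figure to reproduce. The only count to check is 135 + 143 = 278, with 313 − 278 = 35 (11.2%) not analysed.

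**1. Can technique be separated from surgeon?** Code technique as 0 for UC and 1 for MLF, and surgeon likewise. The two columns are identical, so the matrix of intercept, technique and surgeon has 3 columns and rank 2. Only their combined effect can be estimated. Regression, matching or a propensity score would not change this, so the choice of unadjusted tests is not its cause. If the MLF operations were shared among several surgeons, there would still be no described overlap with the UC surgeon.

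**2. The illustration in the concern.** Rates of 10% and 20% are assumed.
- Pooled rate: (13.5 + 28.6)/278 = 0.1514.
- Null standard error: √[0.1514 × 0.8486 × (1/135 + 1/143)] = 0.0430.
- Alternative standard error: √[0.09/135 + 0.16/143] = 0.0423.
- z = (0.10 − 1.96 × 0.0430)/0.0423 = 0.37, which gives a probability of about 0.64.

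**3. Anaesthesia.** This overlap is partial, because some UC patients had spinal anaesthesia. With s UC patients under spinal and 135 − s under local, the technique–anaesthesia correlation is 143(135 − s)/√[135 × 143 × (143 + s)(135 − s)].

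| Assumed UC spinal share | s | Correlation | Variance inflation |
|---|---|---|---|
| 10% | 14 | 0.90 | 5.4 |
| 50% | 68 | 0.58 | 1.5 |
| 90% | 122 | 0.23 | 1.05 |

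Separation is therefore possible in principle (rank 3). To see what a comparison of MLF with spinal-only UC would cost, take an assumed 10% outcome rate and m UC patients. The 95% half-width for a difference is 1.96√[0.09(1/m + 1/143)].

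| UC patients used (assumed share) | m | Half-width, points |
|---|---|---|
| All | 135 | 7.1 |
| 60% | 81 | 8.2 |
| 40% | 54 | 9.4 |
| 20% | 27 | 12.3 |

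The spinal-only UC patients are also those who were unwilling to have, or were steered away from, local anaesthesia. Precision is lost and a new selection enters. Anaesthesia type is not named among the items on the follow-up forms, so its availability is not confirmed. The option of local anaesthesia may also be part of what UC offers, in which case removing it would remove a real effect.

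**4. Early wound contact, days 1 to 14 after surgery.**
- MLF: checks every 2 days after discharge on day 1, 2, 3 or 4 (days assumed) give 6, 6, 5 or 5. Inpatient days are not counted.
- UC: three clinic dressings (one per day assumed), plus visits every 7 to 10 days. Counted from day 0 or day 3, these visits add 1 or 2. Total 4 to 5.

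Counting only from day 4 gives 5–6 against 1–2, which looks far larger because it leaves out the three UC dressings. A gap in frequency after day 3 is real. However, the month of wound surveillance is stated for both groups, and no group difference is described for the telephone contacts.

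**5. Discharge.** The rule in Postoperative care makes same-day discharge 0 of 143 in MLF. Five such UC patients would suffice for significance: (135 × 134 × 133 × 132 × 131)/(278 × 277 × 276 × 275 × 274) = 0.026, which is also the two-sided Fisher value. But hospital stay is not a listed outcome, and the result only restates the discharge rule. It says nothing about bias in healing, readmission, reoperation, revision or satisfaction.

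**The case for a change.** The strongest case for a change is that defining the contrast is the plan's job. The relevant facts are spread over several sections, their joint consequence is stated nowhere, and groups named after operations invite a causal reading. Because the surgeon overlap cannot be repaired, the limit should be written down, and a sentence or two would cost almost nothing.

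Much of this stands. Technique and surgeon are inseparable, patient selection is unaddressed, surgeons recorded the healing and reoperation data, and no limit on attribution is stated. A cautionary sentence in the report would be good practice.

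It still does not amount to a fault in the plan. The text is a short, past-tense methods description with no conclusions section, and it makes no technique-only claim that would need correcting. It says openly that the review is retrospective and that surgeon, anaesthesia and follow-up differ by group. Surgeon recording is also not universal: satisfaction came from questioning the patients.

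**Conclusion.** No change to the plan follows. The confounding of surgeon with technique is complete (rank 2 of 3) and was fixed when the operations were done, so no choice of test can remove it. What remains is a limit on interpretation that a competent analyst would observe when writing up: this is a retrospective, non-randomised comparison of one surgeon's UC practice with another surgeon's MLF practice, and differences are not to be credited to technique alone. Saying so changes no analysis and no result.

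A split by anaesthesia brings no clear gain. At an assumed 10% rate it would widen the interval from 7.1 points to between 8.2 and 12.3 points, depending on the assumed spinal share, and it would compare a selected subset.

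This conclusion rests on reading the MLF sentence as meaning that the UC surgeon did none of the MLF operations, and on the documents making no technique-only claim. A report that credited a difference to the operation itself would go beyond what these data can support.

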## Postoperative care

Patients who underwent the surgery under local anesthesia were discharged on the same day. Patients on whom spinal anesthesia was used stayed in the hospital for 1 or more days.

Antibiotics were not given to the patients in either group. An analgesic containing diclofenac sodium (50 mg bid) was prescribed, and patients were recommended to take it if they experienced pain.

Dressings were changed in the outpatient clinic for the first 3 days in the UC group. Afterward, the process of dressing was explained to the patient's relatives, and the dressing process was continued at home. We called the patient for follow-up at 7–10-day intervals.

In the MLF group, the wound was checked at 2-day intervals after discharge from the hospital. The surgeon removed the sutures after observing for complete wound epithelization. All patients in either group were followed up for wound complications for 1 month after discharge from the hospital.

Patients were contacted via telephone for follow-up at 6 months and 1 year postoperative. Following this, they were then contacted for an annual check. The patients were questioned regarding their degree of satisfaction with the surgery and the postoperative results (graded as excellent, good, not bad, and bad). Surgeons recorded information on treatment, the healing process, follow-up examinations, readmission, reoperation, and revision on follow-up forms.

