### Statistical analyses

All statistical analyses were conducted using SPSS for Windows, version 22 (IBM Corp, Armonk, NY). Firstly, Kolmogorov–Smirnov and Shapiro–Wilk normality tests were performed. If the normality assumption could not be achieved in any group, nonparametric test methods were chosen. Secondly, the Mann–Whitney U test was performed to compare the obtained variables between groups.

The chi-square and Fisher exact tests were used to analyze the relationships or differences of categorical variables between groups.

Comparative results and other demographic characteristics between groups were presented with the ratio of qualitative variables. Quantitative variables are represented by means. A value of  $p < 0.05$  was considered statistically significant.

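### The ordered four-grade satisfaction scale is not assigned a test, and the plan's likelier route, chi-square/Fisher, ignores the order of the grades

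*Combined protocol and SAP*

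**What the plan says.** The Postoperative care section describes telephone contact after surgery: "Patients were contacted via telephone for follow-up at 6 months and 1 year postoperative. Following this, they were then contacted for an annual check". It then says that patients were asked about their "degree of satisfaction with the surgery and the postoperative results (graded as excellent, good, not bad, and bad". This is the only outcome in the document that patients rate themselves. No time point is attached to the question.

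The Statistical analyses section has two routes for comparing groups.

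- **Rank route.** Normality is tested first. Then "If the normality assumption could not be achieved in any group, nonparametric test methods were chosen", and "the Mann–Whitney U test was performed to compare the obtained variables between groups". The variables sent down this route are not listed.
- **Categorical route.** "The chi-square and Fisher exact tests were used to analyze the relationships or differences of categorical variables between groups". For reporting, "Comparative results and other demographic characteristics between groups were presented with the ratio of qualitative variables", and quantitative variables are given as means.

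Ordinal variables, a trend test and an ordinal effect measure are not mentioned. Satisfaction is not named in this section.

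**The concern.** The four grades run from best to worst, and the clinical question is whether patients were more satisfied after one operation than after the other. A four-label grade looks like a categorical variable. The rank test is introduced as the second step after normality testing, which concerns measured quantities. The likelier reading is therefore that satisfaction goes to chi-square or Fisher.

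On a table of two groups by four grades, Pearson chi-square has 3 degrees of freedom and asks only whether the two distributions differ in any way. Its p-value stays the same if the grade labels are shuffled. Two things follow. A real shift towards better grades is more easily missed. And a significant result can arise when one group has more patients at both ends of the scale, which is not a satisfaction advantage. Because the test is not named, the choice is also open until after the ratings have been seen.

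**Working it through.** **Inputs from the document.** Group sizes are 135 (UC) and 143 (MLF), total 278 (Study Population). The significance level is 0.05 (Statistical analyses); sidedness is not stated, so two-sided is assumed. The document gives no power, effect size or grade distribution for satisfaction, so there is no figure of its own to reproduce. All distributions and odds ratios below are assumptions.

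**Step 1: one illustrative table.** Invented counts, best to worst grade: 60/50/17/8 in the group of 135 and 83/44/12/4 in the group of 143. Column totals are 143, 94, 29, 12.

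*Chi-square*, the sum of (observed − expected)²/expected, with expected = column total × group size/278:
- group of 135: 1.284 + 0.415 + 0.604 + 0.810
- group of 143: 1.212 + 0.392 + 0.571 + 0.765
- total 6.05 on 3 df, p = 0.109. Reordering the four columns leaves it unchanged.

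*Tie-corrected Mann–Whitney.* The midranks of the grades are 72, 190.5, 252 and 272.5.
- Rank sum, group of 135: 60×72 + 50×190.5 + 17×252 + 8×272.5 = 20,309
- Expected: 135×279/2 = 18,832.5
- Variance: (135×143/12) × [279 − Σ(t³ − t)/(278×277)], with t the column totals and Σ(t³ − t) = 3,780,630, giving 369,859; SD 608.2
- z = (20,309 − 18,832.5)/608.2 = 2.43, p = 0.015
- Probability that a patient in the group of 143 has the better grade, ties counted half: (20,309 − 135×136/2)/(135×143) = 11,129/19,305 = 0.58

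The same data fall on opposite sides of 0.05, and only the second analysis says which group did better.

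**Step 2: power for a consistent shift.** The second group's grades come from multiplying the odds of being at or above each grade by a common odds ratio (OR). Example: 45/35/12/8% has cumulative proportions 0.45, 0.80, 0.92, so odds 0.818, 4, 11.5. Times 1.75 gives 1.432, 7, 20.1, so 0.589, 0.875, 0.953, that is 58.9/28.6/7.8/4.7%. For each scenario 100,000 data sets were simulated at n = 135 and 143. Entries are power of chi-square vs Mann–Whitney, in %.

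| Assumed grades, first group (%) | OR 1.5 | OR 1.75 | OR 2.0 |
|---|---|---|---|
| 45/35/12/8 | 29 vs 43 | 51 vs 68 | 70 vs 85 |
| 30/40/20/10 | 30 vs 45 | 54 vs 71 | 74 vs 88 |
| 25/25/25/25 | 32 vs 47 | 57 vs 74 | 77 vs 89 |
| 40/40/15/5 | 29 vs 43 | 52 vs 69 | 72 vs 86 |
| 60/30/7/3 | 24 vs 37 | 43 vs 60 | 61 vs 78 |

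The gap, from unrounded values, runs from 12 to 17 percentage points. At OR 1.0 both tests reject about 5% of the time. Fisher's test was not simulated; it ignores the order too.

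**Step 3: differences that are not a shift.** The ranking reverses.
- 40/40/15/5 vs 50/28/12/10%: chi-square 61%, Mann–Whitney 15%. The probability of a better grade in the second group, ties half, is 0.53.
- 30/40/20/10 vs 40/20/25/15%: chi-square 89%, Mann–Whitney 5%. That probability is 0.28 + 0.06 + 0.06 + 0.04 + 0.025 + 0.025 + 0.0075 = 0.4975, so neither group is better on balance, yet chi-square is usually significant.

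**The case against.** The strongest reply is that no sentence in the plan prescribes the wrong test. A reader might infer that chi-square/Fisher is the plan's only method for graded variables. The text does not support that: the Statistical analyses section also names a rank test for unlisted variables and assigns satisfaction to neither. This stands. The routing to chi-square is the likelier reading, not a stated rule.

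A reader might also infer that chi-square always loses power here. Step 3 shows otherwise. The loss holds for a consistent shift, the pattern for which a rank test is built. This stands too, although in the second Step 3 example a significant chi-square result would not answer whether patients were more satisfied.

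Third, the plan reports qualitative variables as ratios, so grade percentages by group would probably be shown and the direction could be seen by eye. That is partly right: the p-value has no direction, but the table would show one. What is missing is a directional estimate with its uncertainty.

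Finally, a reader might take the scale to have been asked at every telephone call. The document describes the calls and then the question in separate sentences and does not link them. It supports only that the time point of the analysed rating is not stated.

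**Conclusion.** The point holds in limited form. The scale is ordered, the plan assigns it no test, and the rule that most naturally applies ignores the order and yields a p-value without direction. For a consistent shift with a common odds ratio of 1.5 to 2.0 at the study's group sizes, that costs about 12 to 17 percentage points of power. This rests on assumed grade distributions, a two-sided 0.05 level and one rating for every patient. It is not a measured loss in this study, and it reverses for some differences that are not a shift.

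The document gives satisfaction no status as a primary or secondary endpoint, so this is a cheap and worthwhile clarification rather than a flaw in the main comparison. A special rule that takes the last rating before any reoperation is not recommended: it would leave patients reoperated before the 6-month call without a rating and could discard dissatisfaction caused by failure of the index operation.

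**What to change.** In the Statistical analyses section, state that:

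1. Satisfaction is an ordered four-level variable, compared between UC and MLF with the tie-corrected Mann–Whitney U test already in the plan, or with the linear-by-linear trend test.
2. The effect is given with direction and a 95% confidence interval: either the probability of a better grade with ties counted half, or a common odds ratio from an ordinal logistic model. The model would be an addition to the plan; neither test in item 1 produces that odds ratio.
3. The percentages in all four grades are shown by group.
4. One rating per patient is used, from a single named time point where the records hold it, with the number of patients without a rating reported in each group.

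The cost is a few sentences and a re-run of one comparison. Item 4 depends on whether ratings were stored with dates: satisfaction is not among the items that the Postoperative care section lists for the follow-up forms, so this must be checked in the records. The statistical downside is lower sensitivity to differences that are not a shift, which the table in item 3 makes visible.

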### Statistical analyses

All statistical analyses were conducted using SPSS for Windows, version 22 (IBM Corp, Armonk, NY). Firstly, Kolmogorov–Smirnov and Shapiro–Wilk normality tests were performed. If the normality assumption could not be achieved in any group, nonparametric test methods were chosen. Secondly, the Mann–Whitney U test was performed to compare the obtained variables between groups.

The chi-square and Fisher exact tests were used to analyze the relationships or differences of categorical variables between groups.

Comparative results and other demographic characteristics between groups were presented with the ratio of qualitative variables. Quantitative variables are represented by means. A value of  $p < 0.05$  was considered statistically significant.

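### Two non-randomised surgical groups are compared only with unadjusted tests, so patient mix alone can give p<0.05; surgeon and early follow-up schedule are fully confounded with group, anaesthesia only partly

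*Combined protocol and SAP*

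**What the plan says.** **Design.** The Study Population section states: "This study retrospectively reviewed the data of 313 patients". The analysed patients "were divided into the UC group (n, 135) and rhomboid excision and MLF group (MLF group; n, 143) and analyzed". The groups are defined by the operation received; neither randomisation nor any rule for choosing the operation is described.

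**Analysis.** The Statistical analyses section lists normality tests and then two kinds of group comparison: "Secondly, the Mann–Whitney U test was performed to compare the obtained variables between groups", and "The chi-square and Fisher exact tests were used to analyze the relationships or differences of categorical variables between groups". It names no regression, stratification, matching, weighting or covariate list. Baseline data appear only descriptively: "Comparative results and other demographic characteristics between groups were presented with the ratio of qualitative variables".

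**Other differences between the groups.**
- Surgeon (Surgical procedure section, on who operated): "The same surgeon performed all operations in the UC group. Operations in the MLF group were performed by another surgeon who conducted the study".
- Anaesthesia: "Patients in the MLF group were operated on under spinal anesthesia". In UC the choice followed patient preference and the anaesthetist's recommendation, and "The patients who had reservations with local anesthesia were operated under spinal anesthesia". The number of UC patients given spinal is not stated.
- Early follow-up (Postoperative care): MLF wounds were checked every 2 days after discharge. UC patients had 3 days of clinic dressings, then home dressing with follow-up every 7–10 days. Both groups were followed for wound complications for the same 1 month after discharge.

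**The concern.** A Mann-Whitney or chi-square test asks whether two distributions differ. Under randomisation, a difference beyond chance can be put down to what was allocated. Here patients reached an operation by an unstated route, so a prognostic factor that is more common in one group shifts the outcome in that group whatever the operation does. The tests keep their 5% level for the hypothesis of equal distributions. They do not keep it for the question the study is built to ask, which is how two operations compare.

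A table of demographics by group lets a reader see an imbalance but does not take it out of any outcome comparison. A p-value below 0.05 could then be credited to the operation when it reflects who had it, who performed it or how it was followed up. Of these, only recorded patient factors, and to a limited extent anaesthesia, can be addressed by analysis.

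**Working it through.** **The plan's own figure.** 135 + 143 = 278, which agrees with the stated number analysed. No sample-size calculation, effect size, SD or event rate is given, so nothing further can be reproduced.

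**Inputs.** From the documents: n = 135 (UC) and 143 (MLF), and significance at 0.05 (taken as two-sided). Assumed: one binary prognostic factor, its frequency in each group and its effect on the outcome. The operation has no effect in any scenario.

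**Continuous outcome, Mann-Whitney.** If the factor has frequency q1 in UC and q2 in MLF and raises the outcome by s (in SDs within factor level), the means differ by d = (q2 − q1)s. The standard error is SE = √{[1 + s²q1(1−q1)]/135 + [1 + s²q2(1−q2)]/143}. The normal approximation to the rejection rate is P(Z > 1.96 − d/SE) + P(Z < −1.96 − d/SE).

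| Factor, UC vs MLF | s | d | SE | Approximation | Mann-Whitney, simulated |
|---|---|---|---|---|---|
| 20% vs 30% | 0.3 | 0.03 | 0.121 | 5.7% | 5.8% |
| 20% vs 30% | 0.5 | 0.05 | 0.123 | 6.9% | 6.7% |
| 20% vs 30% | 0.8 | 0.08 | 0.127 | 9.7% | 9.4% |
| 20% vs 40% | 0.5 | 0.10 | 0.123 | 12.9% | 12.4% |
| 20% vs 40% | 0.8 | 0.16 | 0.127 | 24.1% | 22.9% |
| 20% vs 50% | 0.5 | 0.15 | 0.123 | 23.0% | 22.5% |
| 20% vs 50% | 0.8 | 0.24 | 0.128 | 46.9% | 46.0% |

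A rank test stratified on the factor (van Elteren) stays at 4.8–5.2%.

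**Binary outcome, chi-square.**
- Weak case: factor 20% vs 30%, risk 10% without it and 20% with it. Group risks are 0.10 + 0.10×0.20 = 0.12 and 0.10 + 0.10×0.30 = 0.13. Rejection is 5.6%, or 3.8% with continuity correction.
- Strong case: factor 20% vs 50%, risk 10% and 30%. Group risks are 0.10 + 0.20×0.20 = 0.14 and 0.10 + 0.20×0.50 = 0.20, a spurious difference of 6.0 points. Rejection is 26%, or 21% with continuity correction. A Mantel-Haenszel test stratified on the factor rejects 4.9%.

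These are illustrations, not bounds. With the factor at 20% vs 60% and risks of 10% and 40%, the chi-square test rejects 68%.

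**Limit of adjustment.** Take the strong case with the recorded factor wrong in 10% of patients.
- Recorded present: UC risk (0.18×0.30 + 0.08×0.10)/0.26 = 0.2385; MLF (0.45×0.30 + 0.05×0.10)/0.50 = 0.2800. Difference 0.0415, weight 35.1×71.5/106.6 = 23.5.
- Recorded absent: UC (0.02×0.30 + 0.72×0.10)/0.74 = 0.1054; MLF (0.05×0.30 + 0.45×0.10)/0.50 = 0.1200. Difference 0.0146, weight 99.9×71.5/171.4 = 41.7.
- Weighted difference 0.024.

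Bias falls from 6.0 to 2.4 points and the adjusted test still rejects 8.1%. With 20% wrong, the figures are 4.1 points and 14.1%.

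**What can be separated from operation.**
- Surgeon: one per group, so surgeon and group are the same variable and no model can split them.
- Early follow-up schedule: set wholly by group, so the same holds.
- Anaesthesia: all MLF patients had spinal and some UC patients did too. Adjusting for anaesthesia then amounts to comparing MLF with the k UC spinal patients, with SE = √(1/143 + 1/k) in SD units. All UC patients (135): 0.120. If k = 68: 0.147. If k = 27: 0.210. Both values of k are assumed.

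**Price of adjustment.** Before any gain from explained outcome variation, the SE of the group difference is multiplied by 1/√(1 − R²), where R² is from regressing group on the covariates. For independent binary factors from 20% vs 30% up to 20% vs 50%, the factor is 1.009–1.055 with one covariate, 1.025–1.161 with three and 1.043–1.258 with five.

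**The case against.** The strongest reply is that no imbalance in any prognostic factor is shown. Every frequency and effect above is assumed, and the results run from about nominal to large. The demographics are tabulated by group, the text makes no explicit causal claim, and covariates chosen now would be chosen after the data exist. All of this stands. It limits what can be said about size, but it does not supply the missing adjustment.

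A second reply is that an open, packed wound and a sutured flap may call for different aftercare, so the schedule could be part of the treatment. That is reasonable. It leads to describing the comparison as one of packages, which the documents do not do.

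Three stronger readings are tempting, and the documents do not support them.
- *That anaesthesia, like surgeon, cannot be adjusted for.* The anaesthesia section describes UC patients who had spinal, so there is overlap with MLF. The real limits are the unstated count and the fact that UC anaesthesia followed preference and recommendation.
- *That the check intervals create an apparent healing difference of 2.5–4 days.* Halving the intervals gives 1 day for MLF and 3.5–5 days for UC. But no healing-time outcome or rule for dating it at a visit is stated. UC also had clinic dressings on the first 3 days, and MLF suture removal was tied to observed epithelization. Unequal checks could shift an outcome dated at a visit; no size should be attached.
- *That the comparison is known to be biased.* The documents give no baseline rates from which to judge this.

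**Conclusion.** The point holds. As written, the plan compares non-randomised groups without adjustment, and p<0.05 can arise from patient mix with no effect of the operation. In the main assumed scenarios the rate of such results runs from about nominal to 46%, resting on a single binary factor and on frequencies and effects that the documents do not give. The actual bias is unknown and could be negligible. Surgeon and early follow-up schedule are fully confounded with group; anaesthesia is partly confounded and can in principle be examined among spinal patients. The shared 1-month wound-complication follow-up narrows the concern about unequal checks. The absence of adjustment is certain; material distortion is possible but not demonstrated. This should be fixed, because a better analysis is available at small cost.

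**What to change.** 1. In the Statistical analyses section, add for each main outcome a comparison adjusted for a short list of baseline variables recorded in the files. Choose the list without reference to outcome results and label it as specified after data collection. Use regression, or propensity-score weighting when events are few. Report it beside the unadjusted result, and do not attribute an unadjusted p<0.05 to the operation unless the adjusted result agrees. If no usable baseline variables are recorded, say so and treat the comparison as descriptive.
2. Report the UC spinal count. If it allows, add a sensitivity comparison restricted to patients operated on under spinal anaesthesia, noting how anaesthesia was chosen in UC.
3. State that results are associations between two packages (operation with its surgeon and early follow-up schedule), not effects of technique alone.

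**Cost.** Wording and reanalysis of existing files, feasible only for variables actually recorded, which the documents do not list. The SE rises by about 1–6% with one covariate and 4–26% with five, before any gain from explained variation. Covariates are chosen after the data exist. Overlap weighting, if used, shifts the target to patients who could have had either operation and adds no outcome information when events are few. Residual confounding remains, and the conclusion is narrower.
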